4.2. Inclusion criteria

Patients should corresponds to all inclusion criteria listed below:

- 1. Signed Informed Consent Form;
- 2. Males and females aged 18 to 75 years old (inclusive);
- 3. Abdominal pain and bloating/flatulence due to functional bowel disorder (including IBS, chronic functional constipation, chronic functional diarrhea or functional abdominal bloating);
- 4. Episodes of abdominal pain for at least 3 months, with a frequency of at least 3 times a month:
- 5. Abdominal pain intensity of 4 to 9 points (inclusive) when assessed on the NRS-11 scale (i.e. weekly average, with daily recording of the worst pain for the last 24 hours during last week of Screening and Run-in period);
- 6. Bloating/flatulence intensity of of 4 to 9 points (inclusive) when assessed on the NRS-11 scale (i.e. weekly average, with daily recording of the worst bloating episode for the last 24 hours during last week of Screening and Run-in period);
- 7. Patients' consent to use adequate contraception methods throughout the study. Adequate contraception methods include:
 - a. oral contraceptives or contraceptive patches,
 - b. condom or diaphragm (barrier method) with spermicide, or
 - c. an intrauterine device

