6.8. Numeric range scale (NRS-11)

NRS-11 is a Visual Analog Scale version (Visual Analog Scale for pain). The scale is a horizontal 10 cm line with the numbers from 0 to 10 located on it, where 0 is "no pain/bloating", 10 is "most severe pain/bloating you can imagine". During Visit 1 (screening and run-in period), the Investigator will train the patient to select a number from 0 to 10 that corresponds to his/her worst pain in the last 24 hours and the greatest bloating/flatulence. Abdominal pain and bloating/flatulence according to the NRS-11 scales will be evaluated at the screening visit, then daily throughout the screening/run-in and study treatment periods (in the Patient's Diary). The Patient's Diary is to be returned to the Site at Visit 3 (Week 4) and stored along with the primary patient's documents. The Investigator should enter the diary data into the eCRF. The baseline parameters of abdominal pain intensity and bloating/flatulence severity for the inclusion criteria assessment will be determined as the average daily NRS-11 scales scores 7 days before randomization (last week of the run-in period).

NRS-11 scales for abdominal pain and bloating/flatulence are provided in Appendix 2.

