9.7.3. Secondary efficacy end points

- Change from baseline of NRS-11 pain intensity after 4 weeks of treatment
- Proportion of patients with the NRS-11 pain intensity reduction of ≥30% versus baseline during at least 50% of treatment weeks over treatment period
- Proportion of patients with the NRS-11 pain intensity reduction of $\geq 50\%$ versus baseline during at least 50% of treatment weeks over treatment period.
- Proportion of patients with the abdominal pain assessed in the Patient Dairy completely resolved during at least 50% of treatment weeks over treatment period (NRS-11 0 assessment).
- Change from baseline of NRS-11 bloating/flatulence intensity after 4 weeks of treatment
- Proportion of patients with the NRS-11 bloating/flatulence intensity reduction of ≥30% versus baseline during at least 50% of treatment weeks over treatment period.
- Proportion of patients with the NRS-11 bloating/flatulence intensity reduction of \geq 50% versus baseline during at least 50% of treatment weeks over treatment period.

Confidential Page 69 of 94

- Proportion of patients with the bloating/flatulence assessed in the Patient Dairy completely resolved during at least 50% of treatment weeks over treatment period (NRS-11 0 assessment).
- For patients with constipation: proportion of patients with any increase in number of CSBM per week versus baseline during at least 50% of treatment weeks.
- For patients with diarrhea: proportion of patients with any decrease in the number of days per week with at least one stool consistency of Type 6 or Type 7 BSS versus baseline during at least 50% of treatment weeks.
- Change in number of days per week during study treatment period when drotaverine was taken.
- Change in quality of life evaluation using IBSQOL questionnaire versus baseline.

The baseline abdominal pain and bloating/flatulence intensity will be determined as average of the worst daily episodes NRS-11 assessment during 7 days before randomization (last week of screening and run-in period). The data from last week of screening and run-in period will be also used for baseline assessment of stool frequency and consistency and number of days of drotaverin intake. Week 1, Week 2, Week3 and Week 4 assessments are the same (data from the last 7 days of the corresponding week).

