4.2.2 Secondary efficacy analysis

The secondary efficacy data are:

- Change from baseline of NRS-11 pain intensity after 4 weeks of treatment
- Proportion of patients with the NRS-11 pain intensity reduction of ≥30% versus baseline during at least 50% of treatment weeks over treatment period
- Proportion of patients with the NRS-11 pain intensity reduction of \geq 50% versus baseline during at least 50% of treatment weeks over treatment period.
- Proportion of patients with the abdominal pain assessed in the Patient Dairy completely resolved during at least 50% of treatment days over treatment period (NRS-11 0 assessment).
- Change from baseline of NRS-11 bloating/flatulence intensity after 4 weeks of treatment
- Proportion of patients with the NRS-11 bloating/flatulence intensity reduction of \geq 30% versus baseline during at least 50% of treatment weeks over treatment period.
- Proportion of patients with the NRS-11 bloating/flatulence intensity reduction of \geq 50% versus baseline during at least 50% of treatment weeks over treatment period.
- Proportion of patients with the bloating/flatulence assessed in the Patient Dairy completely resolved during at least 50% of treatment days over treatment period (NRS-11 0 assessment).
- Change in number of days per week during study treatment period when drotaverine was taken.
- Change in quality-of-life evaluation using IBS-QOL questionnaire versus baseline.

Secondary endpoints "Change from baseline of NRS-11 pain intensity after 4 weeks of treatment", "Change from baseline of NRS-11 bloating/flatulence intensity after 4 weeks of treatment" and "Change in quality-of-life evaluation using IBS-QOL questionnaire versus

baseline" will be compared between the two treatment groups by means of analysis of covariance (ANCOVA), with treatment, site as fixed effects and baseline value (if available) as covariate. The same SAS code with MIXED procedure as for primary endpoint will be used for these endpoints.

Secondary endpoint "Change in number of days per week during study treatment period when drotaverine was taken" will be compared between the two treatment groups by means of analysis of variance (ANOVA), with treatment, site as fixed effects. To achieve full conformity with ANCOVA in case of missing's the ANOVA analysis will be performed using MIXED procedure as well:

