The baseline abdominal pain and bloating/flatulence intensity will be determined as the average of daily episodes NRS-11 assessment during 7 days before randomization (last week of screening and run-in period, in other words, the average of daily episodes from - 6 to 1 days). The data from the last week of screening and run-in period will be also used for baseline assessment of stool frequency and consistency and number of days of drotaverine intake. Week 1 (average of data 2 - 8 days), Week 2 (average of data 9 - 15 days), Week 3 (average of data 16 - 22 days) and Week 4 (average of data from the last 7 days of the corresponding week in the case duration of treatment 28 days: 23 to 29 days or data from the last 7 days before the last treatment day inclusively in the case duration of treatment did not equal 28 days).

The proportion of patients with the *Scale* reduction of $\geq A\%$ versus baseline during at least 50% of treatment weeks over treatment period must be calculated as:

$$\frac{n_T}{N_T}$$

where N_T is total number of patients in the treatment arm T, n_T is number of patients in the treatment arm T who had reduction of $\ge A\%$ versus baseline (week 0) during at least 2 of treatment weeks over treatment period: week 1, week 2, week 3, week 4). Reduction of $\ge A\%$ must calculate as:

$$Reduction_{i} = \frac{\overline{Scale_{Week_{i}}} - \overline{Scale_{Week_{0}}}}{\overline{Scale_{Week_{0}}}} \times 100 \ge A\%$$

The transformation formula used for the IBS-QOL total and scale scores is:

 $Score = \frac{The sum of the items - lowest possible score}{Possible raw score range} \times 100$

Where

lowest possible score = number of questions \times lowest possible score of the items

possible raw score range

= number of questions

 \times (upper possible score of the items - lowest possible score of the items)

The comparisons of treatment arms for secondary endpoints with "Proportion of patients with the..." type will be analyzed using Fisher exact test. The test will be performed by separately for for Mebeverine + Simethicone combination VS Duspatalin (mebeverin) and Mebeverine + Simethicone combination VS Espumisan (simethicone) comparisons.

Fisher exact test will be performed using following SAS code for the analysis:

```
PROC FREQ DATA = [dataset name];
  weight [frequency var] / ZEROS;
  tables [frequency var lvl 1/ frequency var lvl 2] * [Arm] / exact Fisher;
RUN;
```

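### The SAP's responder formula has its sign reversed, so all four percentage-reduction endpoints would count worsening, not improvement

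*SAP*

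**What the plan says.** Protocol section 9.7.3 defines the first responder endpoint as "Proportion of patients with the NRS-11 pain intensity reduction of ≥30% versus baseline during at least 50% of treatment weeks over treatment period". The same list has a 50% version for pain, and 30% and 50% versions for bloating/flatulence. SAP section 4.2.2 repeats all four as reductions.

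The SAP then turns them into a calculation. A patient counts if the reduction is reached "versus baseline (week 0) during at least 2 of treatment weeks over treatment period: week 1, week 2, week 3, week 4", which fixes week 0 as baseline and sets the bar at two of four weeks. The weekly rule is introduced by "Reduction of $\ge A\%$ must calculate as" and reads "Reduction_{i} = \frac{\overline{Scale_{Week_{i}}} - \overline{Scale_{Week_{0}}}}{\overline{Scale_{Week_{0}}}} \times 100 \ge A", with A standing for 30 or 50. The bars denote weekly means.

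Protocol section 6.8 gives the direction of the scale: 0 is absence of the symptom, and 10 is "most severe pain/bloating you can imagine".

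**The concern.** The formula is labelled a reduction but computes percentage change from baseline, which is positive only when the score rises. Requiring it to be at least +30% or +50% therefore selects weeks of deterioration.

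This is the only derivation the SAP gives for these four endpoints, and it is worded as mandatory. Nothing later corrects it. There is no absolute value and no negative threshold, and the SAS code for Fisher's exact test starts from responder counts that have already been derived.

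The stake is the symptom-specific evidence. Protocol section 3.8.1 relies on the relevant secondary endpoints, alongside the primary, to show what each component contributes. If the rule were programmed as written, the more effective arm would tend to show the lower responder rate. SAP section 4.2.2 also sets p to 1.0000 when a row or column of the table is empty. A comparison in which nobody met the reversed rule would therefore be reported as a null result instead of being recognised as an error.

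**Working it through.** **Inputs from the documents**
- Rule as written (SAP 4.2.2): f = (Wi - W0)/W0 x 100, required to be >= A.
- Endpoint in words (Protocol 9.7.3, SAP 4.2.2): a reduction, so g = (W0 - Wi)/W0 x 100, required to be >= A.
- A = 30 or 50; at least two of four weeks.
- Scale 0 to 10 with 10 worst (Protocol 6.8); eligible baseline weekly means 4 to 9 for each symptom (Protocol 4.2).

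The plan states no numerical result for this rule, so there is no figure to reproduce first.

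**Step 1. Substitution**

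| Baseline | Week mean | f (SAP) | SAP rule met? | g (true reduction) | Endpoint met? |
|---|---|---|---|---|---|
| 6 | 3 | -50% | no | +50% | 30% and 50% |
| 6 | 4.2 | -30% | no | +30% | 30% |
| 4 | 0 | -100% | no | +100% | 30% and 50% |
| 5 | 7 | +40% | 30% | -40% | no |
| 6 | 7.8 | +30% | 30% | -30% | no |
| 6 | 9 | +50% | 30% and 50% | -50% | no |

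Complete resolution fails at both thresholds. Since f = -g, this holds in general: any improved week has f < 0 and cannot qualify, and any week worse by at least A% does qualify.

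**Step 2. Ceiling.** The rule needs Wi >= W0 x (1 + A/100), and Wi cannot exceed 10. It can therefore be met only if W0 <= 10/1.3 = 7.69 (A = 30) or W0 <= 10/1.5 = 6.67 (A = 50). Eligible patients with baselines between those limits and 9 could never be counted, whatever happened to them.

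**Step 3. Patient level.** All four-week patterns were enumerated on an integer grid (baseline 4 to 9, weekly means 0 to 10) under the two-of-four rule. The only true responders also counted by the SAP rule have exactly two weeks improved and two weeks worsened, each by at least A%. They are counted only because of the worsened weeks.

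**Step 4. Illustrative size.** Assumptions: one week, baseline 6, change normally distributed with SD 2.5, mean change -3 in one arm and -2 in the other. The mean changes and the baseline are not from the documents. The SD is the planning value in Protocol 9.2, which is applied there to the sum score; that section also cites about 2.5 for single NRS-11 scales. The thresholds are 0.30 x 6 = 1.8 points and 0.50 x 6 = 3 points.

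- 30%, mean -3: true P(change <= -1.8) = Phi(1.2/2.5) = Phi(0.48) = 68.4%; SAP P(change >= +1.8) = 1 - Phi(4.8/2.5) = 1 - Phi(1.92) = 2.7%.
- 30%, mean -2: true Phi(0.08) = 53.2%; SAP 1 - Phi(1.52) = 6.4%.
- 50%, mean -3: true Phi(0) = 50.0%; SAP 1 - Phi(2.40) = 0.8%.
- 50%, mean -2: true Phi(-0.40) = 34.5%; SAP 1 - Phi(2.00) = 2.3%.

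At 30% the true difference is 68.4 - 53.2 = 15.2 points in favour of the better arm; the SAP rule gives 2.7 - 6.4 = -3.7 points. At 50% the figures are +15.5 and -1.5 points.

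**The case against.** The strongest reply is that the intent is not in doubt. The quantity is named a reduction, the sentence before the formula speaks of a reduction versus baseline, and the protocol agrees. A programmer might follow the words, so the misclassification depends on literal coding. That is fair, and it makes this a contradiction between correct words and a wrong formula. It does not rescue the formula: the SAP makes it mandatory, and two independent programmers who both coded it would agree on the wrong answer.

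Second, the reversal would seldom be statistically convincing. With the illustrative 30% rates, about 8 versus 4 patients of 132 per arm gives a Fisher p of about 0.38, and 10 versus 4 of 155 gives about 0.17. At 50%, 3 versus 1 of 132 gives about 0.62. This stands: the point estimate reverses, but the likelier outcome is near-zero rates and an uninformative test. Such rates beside falling mean scores would probably be noticed.

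Third, the illustration covers one week and one baseline with an unbounded normal, whereas the endpoint needs two of four correlated weeks on a bounded scale. This also stands; the percentages are not expected trial rates. The sign error itself needs no model.

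Fourth, the formula was extracted from a PDF, so a lost symbol cannot be fully excluded. A lost absolute-value bar would not help, because worsening would still count as response.

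**Conclusion.** The concern holds. As written, the SAP rule inverts responder classification for all four percentage-reduction endpoints. Week by week this is exact and rests only on the printed formula and the direction of the scale. By patient, the sole exception is the mixed pattern of two improved and two worsened weeks.

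Under the stated illustrative assumptions, a true advantage of about 15 points becomes an apparent deficit of about 4 points at the 30% threshold and 1.5 points at 50%. The damage to reported results is conditional on literal programming.

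The scope is limited to secondary endpoints. The primary endpoint, the change-from-baseline endpoints and the complete-resolution endpoints do not use this formula, and trial success rests on the two primary comparisons alone. It should still be corrected, because a mandatory rule that yields the opposite of the defined endpoint is wrong as written.

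**What to change.** In SAP section 4.2.2, replace the formula with Reduction_i = (Scale_Week0 - Scale_Week_i)/Scale_Week0 x 100 >= A%. Equivalently, keep the present numerator and require the result to be <= -A%. With the first form, 6 to 3 gives +50% and meets both thresholds, 6 to 4.2 gives +30% and meets the 30% threshold, and 6 to 7.8 gives -30% and fails.

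Check that the program deriving the responder flag matches the corrected line.

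The cost is a one-line SAP change, with no new data, no change to the protocol endpoints and no statistical downside. Protocol section 9.4 has the SAP final before database lock, so the correction belongs before lock. If lock has passed, record it as a change in the study report, as Protocol section 9.10 provides.

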4.3 Safety analysis

The Safety subject sample will be used for the analysis of the safety data. In addition to this, three treatment groups will be used: "Mebeverine+Simethicone fixed-dose combination", "Espumisan® (simethicone)" and "Duspatalin® (mebeverin)".

The gap period is 7 days for adverse events, 7 days for vital signs, laboratory measurements and concomitant medications.

The following dictionaries are used for coding of medical terms:

Medical term	Dictionary	Version
Concomitant medications	WHO DDE	March 2020, or later
Adverse events	MedDRA	23.1
Medical histories	MedDRA	23.1

Treatment Emergent Adverse Events

An AE that starts during a unique treatment or that already exists before the start of that unique treatment but worsens during the treatment or post-treatment period (if no longer than 7 days after last dose of respective treatment) will be considered as treatment emergent for that unique treatment.

The following unique treatments are distinguished: Mebeverine + Simethicone, 135 mg+80 mg, three times a day; Duspatalin 135 mg three times a day; Espumisan, 80 mg (2 capsules 40 mg) three times a day. AEs will be reported on a per-subject basis, i.e., counting subjects rather than events. This means that if a subject suffers the same AEs repeatedly during the applicable study or treatment period, the event will be counted only once for that period. Repeated events per subject will be summarized according to the following rule: if a subject suffered the same AE more than once, the event will be assigned the worst severity, the closest relationship to the study drug and the earliest starting date. Only treatment emergent AEs (TEAE) will be reported. In the listings, however, all occurrences of the AEs will be presented.

For each unique treatment, TEAES will be summarized by MedDRA primary system organ class (SOC), high level term (HLT) within primary SOC and preferred term (PT) within HLT and primary SOC. Severity and drug-event relationship of adverse events are summarized separately.

In the listings, all occurrences of AEs will be presented together with all relevant information from the eCRFs. In addition, TEAEs will be flagged. Start and end day of the AE and the day of last dose of study drug will be also presented, relative to the start day of the treatment under which is started or worsened and relative to start of any study drug.

SAEs leading to death, non-fatal SAEs, TEAEs leading to study termination, TEAEs leading to discontinuation of study drug will be listed separately.

Vital signs, body weight, waist circumference and body mass index (BMI)

Vital signs include systolic blood pressure (SBP), diastolic blood pressure (DBP), and pulse rate.

Vital signs, body weight, waist circumference and BMI including changes from baseline will be summarized with descriptive statistics per treatment group.

Markedly abnormal values will be identified in accordance with pre-defined criteria, as presented in Table 5 in SAP Module 2.

The number and percentage of subjects with any post-baseline markedly abnormal value under treatment will be presented by variable, treatment. Percentages will be based on the total number of subjects with a baseline and post-baseline measurement of the specified variable in the analysis sample. All markedly abnormal values will be listed.

Safety will be assessed per treatment arm, based on the incidence and severity of AE and SAE, physical examination, vital signs and laboratory test results.

Laboratory data

Hematology and biochemistry values will be reported and analyzed in SI units (International System of Units).

Laboratory test results including changes from baseline will be summarized with descriptive statistics by treatment and cohort.

Each observed hematology and biochemistry value will be categorized whether it is lying below, within, or above the laboratory's reference range. These categories (low, normal, high) plus a category for missing values will be cross-tabulated (shift table) for baseline versus all time points. Only subjects with a value at baseline and the respective time point will be included in the shift table.

Markedly abnormal values will be identified in accordance with pre-defined criteria, as presented in Table 2 and 3 in SAP Module 2.

Additionally, a value of INR > 1.5 will be defined as markedly abnormal value.

The number and percentage of subjects with any post-baseline markedly abnormal value under treatment will be presented by laboratory test and treatment. Percentages will be based on the total number of subjects with a post-baseline measurement of the specified laboratory test in the analysis sample.

All markedly abnormal and/or clinically significant values will be listed.

Analysis of safety endpoints:

Safety variables will be summarized descriptively per treatment. Quantitative variables will be described by n, arithmetic mean, SD, minimum and maximum. Qualitative variables will be described by frequency tables containing counts and percentages.

For each unique treatment, treatment emergent AEs will be summarized per primary SOC, per HLT by primary SOC and per PT by HLT and primary SOC. Severity and drug-event relationship of treatment emergent AEs are summarized separately.

Laboratory values, vital signs and their changes from baseline will be summarized by visit in tables of descriptive statistics. Abnormal values (according to the reference ranges) will be presented in frequency tables (low, normal and high values).

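### The laboratory markedly-abnormal table in SAP 4.3 has no baseline condition, so, unless Module 2 supplies one, abnormalities already present at screening are counted with new ones

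*SAP*

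**What the plan says.** Under Laboratory data, SAP 4.3 sets the count as follows: "The number and percentage of subjects with any post-baseline markedly abnormal value under treatment will be presented by laboratory test and treatment". Percentages are based on "the total number of subjects with a post-baseline measurement of the specified laboratory test". The thresholds are held elsewhere: "Markedly abnormal values will be identified in accordance with pre-defined criteria, as presented in Table 2 and 3 in SAP Module 2".

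Three other rules in SAP 4.3 do refer to baseline:

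- **Vital signs.** The numerator has the same form, "any post-baseline markedly abnormal value under treatment", but the denominator is "the total number of subjects with a baseline and post-baseline measurement of the specified variable".
- **Laboratory shift tables.** Low, normal and high categories are "cross-tabulated (shift table) for baseline versus all time points", and "Only subjects with a value at baseline and the respective time point will be included in the shift table".
- **Adverse events.** A pre-existing event is treatment emergent only if it "already exists before the start of that unique treatment but worsens during the treatment" or the post-treatment period.

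The same section plans change-from-baseline summaries and a listing of markedly abnormal or clinically significant values. Safety variables are summarized descriptively; no test is planned on this table.

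**The concern.** Protocol 3.5.1 gives an acceptable safety profile of the combination against each component as a purpose of the trial. The markedly-abnormal table is where a reader will look for uncommon, large laboratory changes by arm. As SAP 4.3 is worded, it combines two groups: subjects who became markedly abnormal on study drug, and subjects who entered that way and did not change. The second group says nothing about the drugs, but it raises the percentage in every arm and can hide how few of the counted subjects are new.

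Such subjects can be enrolled. The exclusion criteria in Protocol 4.3 name fecal calprotectin, HIV and hepatitis B and C tests, but set no hematology or biochemistry cut-offs. Otherwise they rely on diagnoses and on the investigator's judgement of significant disease. Patients up to 75 years are eligible.

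**Working it through.** The plan states no figure on this point, so there is none to reproduce. The check has two parts.

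**1. Can another planned display give the per-arm proportion with a new marked abnormality?**

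- *Shift tables:* the categories follow the reference range. A change from mildly high to markedly high is high-to-high, and so is markedly high throughout. New and pre-existing marked abnormalities cannot be separated.
- *Change-from-baseline summaries:* these are group statistics, in which a few outliers do not show.
- *Listings:* they hold the individual values but give no rate by arm.
- *Adverse events:* Protocol 6.11 sends only clinically significant laboratory abnormalities to the AE form, so the rest are missed.

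No table described in SAP 4.3 gives that proportion.

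**2. How much could it matter?**

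From the documents: 155 patients per arm (Protocol 9.2), with hematology and biochemistry at Visit 1 and at Visit 3 or early discontinuation (Protocol Table 1). Everything else is assumed: *b*, the share markedly abnormal at baseline (0 to 10%); *s*, the share of these still abnormal after baseline (50% or 100%); and *i*, the incidence of new marked abnormality (1% against 5%). *b* and *s* are taken as equal in the two arms.

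- Rate in the table as worded: b·s + (1 − b)·i
- Rate among subjects not markedly abnormal at baseline: i
- Risk difference as worded: (1 − b)·(i₁ − i₀), whatever the value of s

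For b = 5% and s = 1: 0.05 + 0.95 × 0.01 = 5.95% and 0.05 + 0.95 × 0.05 = 9.75%. The ratio is 9.75/5.95 = 1.64 and the difference 3.80 points.

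| b | Rates as worded (s = 1) | Difference, points | Ratio, s = 1 | Ratio, s = 0.5 | Pre-existing share of the lower-rate arm's count (s = 1) |
|---|---|---|---|---|---|
| 0% | 1.00% v 5.00% | 4.00 | 5.00 | 5.00 | 0% |
| 1% | 1.99% v 5.95% | 3.96 | 2.99 | 3.66 | 50% |
| 2% | 2.98% v 6.90% | 3.92 | 2.32 | 2.98 | 67% |
| 5% | 5.95% v 9.75% | 3.80 | 1.64 | 2.10 | 84% |
| 10% | 10.90% v 14.50% | 3.60 | 1.33 | 1.61 | 92% |

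Restricted to subjects not markedly abnormal at baseline, every row shows 1% against 5%: ratio 5.0, difference 4.0 points. With new incidences of 2% and 6% (true ratio 3.0) and b = 5%, the ratio as worded is 1.55 at s = 1 and 1.86 at s = 0.5.

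*Noise*, at b = 5% and s = 1. Standard error of the difference as worded, 155 per arm: √[(0.0595 × 0.9405 + 0.0975 × 0.9025)/155] = 3.05 points. Restricted, 155 × 0.95 = 147.25 per arm: √[(0.01 × 0.99 + 0.05 × 0.95)/147.25] = 1.97 points. The difference is then 3.80/3.05 = 1.2 standard errors as worded and 4.00/1.97 = 2.0 when restricted.

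**The case against.** **Module 2 may already settle it.** The criteria are in a module that was not available. A reader might infer from SAP 4.3 that pre-existing abnormalities are certain to be counted; the documents do not support that. If the laboratory criteria include a change from baseline, a stable value would not qualify. Against this, a denominator that needs no baseline value fits poorly with a change-based criterion. The point therefore stands only conditionally.

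**Requiring a baseline value would not cure it.** This is correct: a subject markedly abnormal at baseline has a baseline value. The gap is that neither numerator nor denominator looks at what that value was.

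**The difference between arms survives.** A reader might infer that a true drug effect is pulled towards nothing. On the difference scale it is not: the difference shrinks only by the factor 1 − b. What suffers is the ratio, the absolute rate and the precision. The SAP reports counts and percentages and plans no ratio or test here.

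**Other displays use baseline.** A reader might take this table as the whole laboratory safety summary. It is not: Protocol 9.8.2 asks for change-from-baseline statistics and low/normal/high tables, and this table is an SAP addition. Clinically significant laboratory changes also reach the AE tables, where the worsening rule applies. That narrows the gap to the proportion newly markedly abnormal but does not close it.

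**Vital signs.** A reader might extend the same criticism to that table. The documents support less there: its denominator requires a baseline value, which is at least consistent with a change-based criterion in Module 2. What remains is whether its numerator is limited to the same subjects.

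**Prevalence may be low.** Cirrhosis, hepatitis B and C and significant concomitant disease are excluded, and with one planned post-baseline blood sample some baseline abnormalities will have resolved. Both would reduce the effect.

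**Conclusion.** The point holds for the laboratory table, as a minor one. As worded, SAP 4.3 counts marked abnormalities without regard to baseline, and no other table it describes separates new from pre-existing ones. If Module 2 adds no baseline or change condition, the absolute rate is overstated in every arm, the ratio is compressed and the comparison is noisier, while the risk difference is nearly kept.

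The size cannot be derived from the documents. Over an assumed baseline prevalence of 1 to 10%, a true ratio of 5.0 would appear as 3.0 down to 1.3 with full persistence, or 3.7 down to 1.6 with half persisting; the difference would go from 4.0 to between 3.96 and 3.60 points. At zero prevalence the two ways of counting agree. These figures rest on assumed incidences and on equal prevalence and persistence in the arms, as randomization would give on average if persistence is unaffected by treatment. The primary analysis is not touched.

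**What to change.** In SAP 4.3, under Laboratory data:

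1. State whether the Module 2 laboratory criteria depend on the baseline value.
2. Present the markedly-abnormal table by baseline status. The main row gives subjects with a new marked abnormality, among those with a baseline value not markedly abnormal in the same direction and at least one post-baseline value of that test.
3. Add separate rows for subjects already markedly abnormal at baseline and for those with no baseline value, so that the count as now defined can still be recovered.

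For vital signs, only confirm that the numerator is limited to the subjects in the stated denominator.

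The cost is a few sentences, one programming filter and some extra rows in a descriptive table. No new data are needed, since blood tests are scheduled at Visits 1 and 3. The drawback is that a few subjects per test leave the main denominator: at an assumed 2 to 5% baseline prevalence, about 3 to 8 of 155 per arm (155 × 0.02 = 3.1; 155 × 0.05 = 7.75).
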